1.2. Schema

Not applicable.

1.3. Schedule of Activities

The SoA table provides an overview of the protocol visits and procedures. Refer to the [Study Assessments and Procedures](#) section of the protocol for detailed information on each procedure and assessment required for compliance with the protocol.

The investigator may schedule visits (unplanned visits) in addition to those listed in the SoA table, in order to conduct evaluations or assessments required to protect the well-being of the participant.

An unplanned potential COVID-19 illness visit and unplanned potential COVID-19 convalescent visit are required at any time between Visit 1 (Vaccination 1) and Visit 8 (6-month postdelivery visit, the final study visit) that potential COVID-19 symptoms are reported, including MIS C.

1.3.1. Schedule of Activities for Maternal Participants

Visit Number (Maternal Participants)	1	2	3	4	5	6	7	8	Unplanned	Unplanned
Visit Description	Screening: -28 Days to Vaccination 1	Vaccination 2	2-Week Post-Vaccination 2 Follow-up ^a	1-Month Post-Vaccination 2 Follow-up ^a	Delivery	1-Week Postdelivery Follow-up Call	1-Month Postdelivery Follow-up ^b	6-Month Postdelivery Follow-up For Participants Originally Randomized to Receive BNT162b2	Potential COVID-19 Illness Visit ^c	Potential COVID-19 Convalescent Visit
Visit Window (Days)	Day 1 Visit 1	19 to 23 Days After Visit 1	11 to 17 Days After Visit 2	28 to 35 Days After Visit 2	Varies	7 to 10 Days After Delivery	21 to 35 Days After Delivery	160 to 200 Days After Delivery	Optimally Within 3 Days After Potential COVID-19 Illness Onset	28 to 35 Days After Potential COVID-19 Illness Visit
Type of Visit	Clinic	Clinic	Clinic	Clinic	Hospital	Phone Call	Clinic	Clinic		
Obtain informed consent	X									
Assign single participant identifier	X									
Obtain demography	X									

Visit Number (Maternal Participants)	1	2	3	4	5	6	7	8	Unplanned	Unplanned
Visit Description	Screening: -28 Days to Vaccination 1	Vaccination 2	2-Week Post-Vaccination 2 Follow-up ^a	1-Month Post-Vaccination 2 Follow-up ^a	Delivery	1-Week Postdelivery Follow-up Call	1-Month Postdelivery Follow-up ^b	6-Month Postdelivery Follow-up For Participants Originally Randomized to Receive BNT162b2	Potential COVID-19 Illness Visit ^c	Potential COVID-19 Convalescent Visit
Visit Window (Days)	Day 1 Visit 1	19 to 23 Days After Visit 1	11 to 17 Days After Visit 2	28 to 35 Days After Visit 2	Varies	7 to 10 Days After Delivery	21 to 35 Days After Delivery	160 to 200 Days After Delivery	Optimally Within 3 Days After Potential COVID-19 Illness Onset	28 to 35 Days After Potential COVID-19 Illness Visit
Type of Visit	Clinic	Clinic	Clinic	Clinic	Hospital	Phone Call	Clinic	Clinic		
Record current alcohol and tobacco usage	X									
Obtain medical history, including obstetric and gestational history	X									
Phase 3 only: For participants who are HIV-positive, record latest CD4 count and HIV viral load	X		X	X	X		X	X		
Record LMP and EDD	X									
Measure vital signs	X	X		X						
Perform physical examination	X									
Perform targeted physical examination		X		X						
Perform obstetric examination	X	X		X						
Perform obstetric ultrasound	X									
Record nonstudy vaccine information	X	X	X	X	X	X	X	X		
Record concomitant medication associated with an adverse event or serious adverse event	X	X	X	X	X	X	X	X ^d		
Record prohibited medications									X	X

PFIZER CONFIDENTIAL

Visit Number (Maternal Participants)	1	2	3	4	5	6	7	8	Unplanned	Unplanned
Visit Description	Screening: -28 Days to Vaccination 1	Vaccination 2	2-Week Post-Vaccination 2 Follow-up ^a	1-Month Post-Vaccination 2 Follow-up ^a	Delivery	1-Week Postdelivery Follow-up Call	1-Month Postdelivery Follow-up ^b	6-Month Postdelivery Follow-up For Participants Originally Randomized to Receive BNT162b2	Potential COVID-19 Illness Visit ^c	Potential COVID-19 Convalescent Visit
Visit Window (Days)	Day 1 Visit 1	19 to 23 Days After Visit 1	11 to 17 Days After Visit 2	28 to 35 Days After Visit 2	Varies	7 to 10 Days After Delivery	21 to 35 Days After Delivery	160 to 200 Days After Delivery	Optimally Within 3 Days After Potential COVID-19 Illness Onset	28 to 35 Days After Potential COVID-19 Illness Visit
Type of Visit	Clinic	Clinic	Clinic	Clinic	Hospital	Phone Call	Clinic	Clinic		
Review eligibility criteria	X	X								
Review temporary delay criteria	X	X								
Review continued eligibility			X	X	X	X	X	X		
Explain/review participant communication methods (including for e-diary completion), assist the participant with downloading the app, or issue provisioned device, if required	X									
Record systemic events at baseline in the e-diary	X									
Assign participant randomization and container number	X									
Collect blood sample for immunogenicity assessment (~20 mL per blood sample)	X	X ^e	X	X	X			X		X
Obtain nasal (midturbinate swab)	X	X							X ^d	
Administer study intervention	X	X								

Visit Number (Maternal Participants)	1	2	3	4	5	6	7	8	Unplanned	Unplanned
Visit Description	Screening: -28 Days to Vaccination 1	Vaccination 2	2-Week Post-Vaccination 2 Follow-up ^a	1-Month Post-Vaccination 2 Follow-up ^a	Delivery	1-Week Postdelivery Follow-up Call	1-Month Postdelivery Follow-up ^b	6-Month Postdelivery Follow-up For Participants Originally Randomized to Receive BNT162b2	Potential COVID-19 Illness Visit ^c	Potential COVID-19 Convalescent Visit
Visit Window (Days)	Day 1 Visit 1	19 to 23 Days After Visit 1	11 to 17 Days After Visit 2	28 to 35 Days After Visit 2	Varies	7 to 10 Days After Delivery	21 to 35 Days After Delivery	160 to 200 Days After Delivery	Optimally Within 3 Days After Potential COVID-19 Illness Onset	28 to 35 Days After Potential COVID-19 Illness Visit
Type of Visit	Clinic	Clinic	Clinic	Clinic	Hospital	Phone Call	Clinic	Clinic		
Assess acute reactions for at least 30 minutes after study intervention administration	X	X								
Provide/ensure participant has a thermometer and measuring device	X	X								
Review reactogenicity e-diary data (daily review is optimal during the active diary period of 7 days following study intervention administration)	↔	↔								
Review ongoing reactogenicity e-diary symptoms with participant and obtain stop dates		X	X							
Record pregnancy outcome information					X	X				
Record AEs and SAEs as appropriate ^f	X	X	X	X	X ^d	X	X ^d	X ^d	X ^d	X ^d
Collect e-diary or assist the participant to delete application								X		

Visit Number (Maternal Participants)	1	2	3	4	5	6	7	8	Unplanned	Unplanned
Visit Description	Screening: -28 Days to Vaccination 1	Vaccination 2	2-Week Post-Vaccination 2 Follow-up ^a	1-Month Post-Vaccination 2 Follow-up ^a	Delivery	1-Week Postdelivery Follow-up Call	1-Month Postdelivery Follow-up ^b	6-Month Postdelivery Follow-up For Participants Originally Randomized to Receive BNT162b2	Potential COVID-19 Illness Visit ^c	Potential COVID-19 Convalescent Visit
Visit Window (Days)	Day 1 Visit 1	19 to 23 Days After Visit 1	11 to 17 Days After Visit 2	28 to 35 Days After Visit 2	Varies	7 to 10 Days After Delivery	21 to 35 Days After Delivery	160 to 200 Days After Delivery	Optimally Within 3 Days After Potential COVID-19 Illness Onset	28 to 35 Days After Potential COVID-19 Illness Visit
Type of Visit	Clinic	Clinic	Clinic	Clinic	Hospital	Phone Call	Clinic	Clinic		
Collection of COVID-19-related clinical and laboratory information (including local diagnosis)									X	X

Abbreviations: EDD = estimated delivery date; HIV = human immunodeficiency virus; LMP = last menstrual period.

- The 2-week postvaccination follow-up and 1-month postvaccination follow-up visits will not be performed if delivery occurs before the visits. If delivery occurs before Vaccination 2, the second dose should be given as soon as possible after delivery. Once delivery occurs, the visit windows are calculated based on the delivery date.
- All maternal participants will be unblinded. Placebo recipients will be given BNT162b2 and move to follow the procedures in [Section 1.3.2](#).
- The COVID-19 illness visit may be conducted as an in-person or telehealth visit.
- Only AEs occurring up to 48 hours after each blood draw and nasal midturbinate swab collection must be recorded.
- Prevaccination blood samples for immunogenicity will be drawn from maternal participants in Phase 2 only.
- The investigator and site staff will ensure the active elicitation and collection of AEs and SAEs through 1 month after Vaccination 2. From 1 month after Vaccination 2 until the 6-month postdelivery follow-up, SAEs will be collected.

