1.3.2. Schedule of Activities for Maternal Participants Who Were Originally Assigned to Placebo

Visit Number (Maternal Participants)	101	102	103
Visit Description	1-Month Postdelivery Follow-up Vaccination 3	Vaccination 4	1-Month Telephone Contact Follow-up
Visit Window (Days)	21 to 35 Days After Delivery	19 to 23 Days After Visit 101	28 to 35 Days After Visit 102
Type of Visit	Clinic	Clinic	Phone Call
Confirm the participant originally received only placebo at Vaccination 1/2. Secondary confirmation by another site staff member is required	X		
Collect prohibited medication use	X	X	X
For participants who are HIV-positive, record latest CD4 count and HIV viral load			X
Review and consider eligibility	X	X	
Review temporary delay criteria	X	X	
Collect blood sample for immunogenicity assessment	~20 mL		
Obtain nasal (midturbinate) swab	X	X	
Obtain vaccine vial allocation via IRT	X	X	
Administer BNT162b2	X	X	
Assess acute reactions for at least 30 minutes after study intervention administration	X	X	
Collect AEs and SAEs as appropriate	X	X	X
Contact the participant by telephone			X

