3. OBJECTIVES, ESTIMANDS, AND ENDPOINTS

Objectives ^a	Estimands	Endpoints
Primary Safety	Primary Safety	Primary Safety
To describe the safety and tolerability of prophylactic BNT162b2 when administered to maternal participants 18 years of age or older vaccinated at 24 to 34 weeks' gestation.	In maternal participants receiving at least 1 dose of study intervention from each vaccine group, the percentage of maternal participants reporting: 
 • Local reactions for up to 7 days following each dose • Systemic events for up to 7 days following each dose • AEs from Dose 1 through 1 month after Dose 2 • SAEs from Dose 1 through 1 month after delivery 	
 • Prompted local reactions (redness, swelling, and pain at the injection site) • Prompted systemic events (fever, fatigue, headache, chills, vomiting, diarrhea, new or worsened muscle pain, and new or worsened joint pain) • AEs • SAEs

Objectives^a	Estimands	Endpoints
Primary Immunogenicity	Primary Immunogenicity	Primary Immunogenicity
To describe the immune response to prophylactic BNT162b2 in maternal participants 18 years of age or older vaccinated at 24 to 34 weeks' gestation and reference to the immune response in nonpregnant women 18 years of age or older from the C4591001 study without evidence of past SARS-CoV-2 infection.	In female participants complying with the key protocol criteria (evaluable participants) and no serological or virological evidence (up to 1 month after receipt of the second dose) of past SARS-CoV-2 infection: 
 GMR, estimated by the ratio of the geometric mean of SARS-CoV-2 neutralizing titers in pregnant women to those in nonpregnant women 1 month after Dose 2 	
 SARS-CoV-2 neutralizing titers
To describe the immune response to prophylactic BNT162b2 in maternal participants 18 years of age or older vaccinated at 24 to 34 weeks' gestation and reference to the immune response in nonpregnant women 18 years of age or older from the C4591001 study with and without evidence of prior SARS-CoV-2 infection.	In female participants complying with the key protocol criteria (evaluable participants): 
 GMR, estimated by the ratio of the geometric mean of SARS-CoV-2 neutralizing titers in pregnant women to those in nonpregnant female participants 1 month after Dose 2 	
 SARS-CoV-2 neutralizing titers

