8.3.1. Time Period and Frequency for Collecting AE and SAE Information

The time period for actively eliciting and collecting AEs and SAEs (“active collection period”) for each maternal participant including her fetus begins from the time the maternal participant provides informed consent, which is obtained before participation in the study (ie, before undergoing any study-related procedure and/or receiving study intervention), through and including a minimum of 28 calendar days after the last administration of the study intervention.

In this study, the investigator and site staff will ensure the active elicitation and collection of AEs and SAEs through Visit 4.

From Visit 4 through Visit 8, SAEs will be collected for maternal participants originally randomized to BNT162b2. In addition, AEs occurring up to 48 hours after blood draws and collection of nasal swabs that are related to study procedures must be reported in the CRF.

Additionally, for those maternal participants who originally received placebo but go on to receive BNT162b2 at Visit 101 and Visit 102, AEs and SAEs will be collected through and 1 month after the second dose of BNT162b2 (Visit 103).

For the infant participant, the time period for actively eliciting and collecting nonserious AEs (“active collection period”) begins at birth and continues through and including 1 month after birth. SAEs and AESIs will be collected from birth through and including 6 months of age.

Follow-up by the investigator continues throughout and after the active collection period and until the AE or SAE or its sequelae resolve or stabilize at a level acceptable to the investigator and Pfizer concurs with that assessment.

For maternal participants who are screen failures, the active collection period ends when screen failure status is determined.

If the participant withdraws from the study and also withdraws consent for the collection of future information, the active collection period ends when consent is withdrawn.

If a participant definitively discontinues or temporarily discontinues study intervention because of an AE or SAE, the AE or SAE must be recorded on the CRF and the SAE reported using the Vaccine SAE Reporting Form.

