8.11.1.2. Visit 3 – 2-Week Postvaccination Follow-up (Clinic)

If delivery occurs before this visit, this visit will not be conducted.

- Phase 3 only: For participants who are HIV-infected, record HIV viral load and CD4 count results from the most recent test performed since their last visit (if any).
- Record nonstudy vaccinations as described in [Section 6.5](#).
- Collect and record concomitant medication associated with AE/SAEs.
- Review the participant's reactogenicity e-diary data. Collect stop dates of any reactogenicity e-diary events ongoing on the last day that the reactogenicity e-diary was completed and record stop dates in the CRF if required.
- Ensure and document that the participant is still eligible for continued participation.
- Collect a blood sample (approximately 20 mL) for immunogenicity testing.
- Record AEs and SAEs as described in [Section 8.3](#).
- Ask the participant to contact the site staff or investigator if an emergency room visit or hospitalization occurs.
- Ask the participant to contact the site staff or investigator if the participant experiences acute chest pain, shortness of breath, or palpitations (see [Section 8.14](#)).
- Ask the participant to contact the site staff or investigator (this could be via the COVID-19 illness e-diary) immediately if she experiences any COVID-19 illness symptoms as detailed in [Section 8.13](#).
- Schedule an appointment for the participant to return for the next study visit.
- Complete the source documents.
- The investigator or an authorized designee completes the CRFs.

8.11.1.3. Visit 4 – 1-Month Postvaccination Follow-up Visit (Clinic: 28-35 Days After Visit 2)

If delivery occurs before this visit, this visit will not be conducted.

- Phase 3 only: For participants who are HIV-infected, record HIV viral load and CD4 count results from the most recent test performed since their last visit (if any).
- Measure vital signs (body temperature, pulse rate, and seated blood pressure).

- Perform targeted physical examination evaluating/noting any clinically significant abnormalities within the following body systems: general appearance; skin; head, eyes, ears, nose, and throat; heart; lungs; abdomen; musculoskeletal; extremities; neurological; and lymph nodes. Significant medical and surgical history and abnormal observations from the physical examination will be documented and recorded in the CRF.

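### For women who deliver before Visit 4, the protocol contradicts itself on whether nonserious AEs are recorded to the end of the primary window, and one of the conflicting instructions applies only to the BNT162b2 arm

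*Protocol*

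**What the plan says.** The primary safety endpoint in Protocol Section 3 covers "AEs from Dose 1 through 1 month after Dose 2". Visit 4, 28 to 35 days after Visit 2, would normally close that window. For Visit 3, and in the same terms for Visit 4, the procedures state: "If delivery occurs before this visit, this visit will not be conducted". What remains is Visit 5 (delivery), Visit 6 (a call 7 to 10 days after delivery) and Visit 7 (21 to 35 days after delivery), where all women are unblinded and placebo women move to Visit 101.

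Instructions that restrict collection:
- In the AE row of 1.3.1, Visits 5 and 7 carry footnote d: "Only AEs occurring up to 48 hours after each blood draw and nasal midturbinate swab collection must be recorded". Visit 6 does not. The schedule lists no blood draw or swab at Visit 7.
- Section 8.3.1 says that "the investigator and site staff will ensure the active elicitation and collection of AEs and SAEs through Visit 4". From Visit 4 on it names only SAEs for the BNT162b2 arm, plus procedure-related AEs within 48 hours of a draw or swab.

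Instructions that require full collection:
- Footnote f, on the same AE row: "The investigator and site staff will ensure the active elicitation and collection of AEs and SAEs through 1 month after Vaccination 2".
- Section 8.3.1 sets a minimum of 28 days after the last study dose.
- Section 8.11.1.6 (Visit 7) asks for AEs and SAEs per Section 8.3, with no 48-hour limit.

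For placebo women at Visit 101, the row in 1.3.2 reads "Collect AEs and SAEs as appropriate", with no restricting footnote.

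**The concern.** For these women the Visit 7 cell carries two opposite instructions, and no passage says which governs. The Visit 7 text does not settle it, because it refers back to Section 8.3. There, 8.3.1 holds both the 28-day minimum and an end point at a visit that these women never have.

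The conflict does not fall evenly on the arms. A site that follows the schedule cells has no nonserious AE to record at Visit 7, but has an open instruction at Visit 101 over the same days after delivery. An AE that begins between the Visit 6 call and that visit, inside the primary window, could be captured for a placebo woman and missed for a BNT162b2 woman. The questioning also takes place once allocation is known. The error would lower AE counts in the vaccine arm and so flatter the vaccine. It would affect the AE percentages, the Tier 2 between-group differences and the related and severe AE summaries (SAP 6.1.1.3).

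**Working it through.** There is no figure in the plan to reproduce. The check is day arithmetic on the visit windows, followed by an estimate of how many women are affected.

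**Inputs.** Let D be days from Dose 2 to delivery. Visit 6 falls on day D + 7 to D + 10, and Visit 7 or 101 on day D + 21 to D + 35 (Protocol 1.3.1, 1.3.2). Let W be the end of the window. Neither document gives 1 month in days for women without Visit 4, so W = 28 and W = 35 are both used, from the Visit 4 window (assumption).

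**Formula.** Days of the window left after Visit 6 = max(0, W − Visit 6 day).

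| D | Visit 6 day | Left, W = 28 | Left, W = 35 | Visit 7/101 day |
|---|---|---|---|---|
| 1 | 8–11 | 17–20 | 24–27 | 22–36 |
| 7 | 14–17 | 11–14 | 18–21 | 28–42 |
| 14 | 21–24 | 4–7 | 11–14 | 35–49 |
| 18 | 25–28 | 0–3 | 7–10 | 39–53 |
| 21 | 28–31 | 0 | 4–7 | 42–56 |
| 25 | 32–35 | 0 | 0–3 | 46–60 |
| 28 | 35–38 | 0 | 0 | 49–63 |

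For W = 28, days are left whenever D is below 28 − 10 = 18. They may be left up to D = 20 (28 − 27 = 1), and none are left from D = 21. For W = 35 the same steps give 25, 27 and 28.

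**Can this happen at term?** Dose 1 is allowed up to 34 0/7 weeks (238 days) and Dose 2 follows 19 to 23 days later. That puts Dose 2 at 257 to 261 days, or 36 5/7 to 37 2/7 weeks. Eighteen days later is 39 2/7 to 39 6/7 weeks. An ordinary term delivery after late enrolment is therefore enough.

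**How many women?** The documents give no distribution of delivery timing, so this rests on assumptions:
- 200 women enrolled over 27 to 34 weeks and 150 over 24 to 34 weeks, either uniformly or weighted to later weeks;
- delivery normally distributed, mean 38.8 to 39.6 weeks, SD 1.4 to 1.8 weeks;
- Dose 2 at day 21, or one day after delivery if delivery came first;
- Visit 6 at 8.5 days after delivery.

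Across 12 simulated combinations with W = 28:
- 19 to 45% deliver before Dose 2 + 28 days;
- 8 to 27% have window days left after Visit 6, with a mean of 6.4 to 9.3 days among those women;
- averaged over all women, this is 1.1 to 5.1% of the 21 + 28 = 49-day window.

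With W = 35, 17 to 41% have days left.

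**Which AEs could be counted unequally?** Only those with onset after Visit 6, inside the window and before Visit 101. SAP 5.2.1 and 6.4 summarize open-label AEs separately. At D = 7, Visit 101 falls on day 28 at the earliest, so with W = 28 the whole exposed stretch precedes it. If delivery precedes Dose 2, Visit 7 or 101 and the unblinding can fall inside the window, and the same conflict applies.

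**The case against.** The strongest reply is that full collection is required. Footnote f has no exception by arm or delivery, the 28-day minimum in 8.3.1 runs from the last dose, and 8.11.1.6 has no 48-hour limit and reads much like the Visit 101 text in 8.17.1. Section 8.3.1.2 requires every nonserious AE in the active collection period to be recorded, and SAP 3.1.1.4 repeats the window. This stands. A reader might infer from footnote d that the BNT162b2 arm has no unrestricted AE collection at the end of the window, or that differential ascertainment is built into the design. The documents do not support either inference: the misstep needs a site to follow footnote d over the other passages.

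The placebo contrast is also narrow. SAP 3.1.1.4 starts the placebo women's additional AE period at their first BNT162b2 dose. Against that, the risk table in Protocol 2.3.1 describes AE collection for these women from consent to Visit 103 without a break, so AEs with onset before Visit 101 remain exposed to uneven practice.

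The scale is modest. The unrestricted Visit 6 call closes the window for many women who miss Visit 4, so 19 to 45% is not the affected group. SAEs and the 7-day e-diary are not touched.

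Last, a change to collection comes late. Enrolment ended on 25 October 2021. Allowing 28 days of screening, Dose 2 at 42 days (the SAP's evaluable limit) and a 35-day month gives 28 + 42 + 35 = 105 days, or about 7 February 2022. SAP version 3 is dated 31 March 2022. This stands too, and is why the SAP step matters most.

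**Conclusion.** The point holds as a contradiction that could make AE ascertainment depend on arm in a primary safety endpoint. It does not show that collection was absent or that the arms did differ. Footnote d at Visits 5 and 7 and the Visit 4 end point in 8.3.1 conflict with footnote f, the 28-day minimum and 8.11.1.6, and the restriction has no counterpart at Visit 101.

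The exposure is confined to deliveries within about 18 to 20 days of Dose 2 (28-day month) or 25 to 27 days (35-day month), and to nonserious AEs with onset between the Visit 6 call and Visit 7 or 101. The day counts follow from the visit windows alone. The 8 to 27% share (28-day month) depends on assumed enrolment and delivery timing and is not trial data. The passages should be reconciled, and the analysis should show whether the result depends on the exposed days.

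**What to change.** Reconcile the passages by AE onset date. A rule based on visit date would not work: with delivery 7 days after Dose 2, Visit 7 falls on days 28 to 42, so a footnote kept for visits beyond day 28 would still block most of the recall needed.

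Protocol:
- In 1.3.1, apply footnote d only to AEs with onset later than 1 month after Dose 2.
- In 8.3.1, end active collection at Visit 4 or, where Visit 4 is not held, at the first contact on or after 1 month following Dose 2.
- At Visits 5, 6 and 7/101, record all AEs with onset up to that day, in the same way in both arms.

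SAP:
- Define 1 month after Dose 2 in days for women without Visit 4.
- For data already collected, add a sensitivity analysis of the primary AE endpoint. For women without Visit 4, count AEs in both arms only up to the Visit 6 contact or the end of the window, whichever is earlier.

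The cost is one footnote, one sentence in 8.3.1, one window rule and one extra table. No visit is added. The downside is a few more nonserious postpartum AEs on record.
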